## **Assessment Overview**

Viral load of AdV will be measured at the central laboratory at each visit from blood and stool samples and at Day -21 to -1 and Day 29 from nasopharyngeal swab. Blood specimens collected should be analyzed by the central laboratory for screening purposes, however, local laboratory results available up to 5 days prior to and/or during screening will be acceptable to determine eligibility. For the inclusion criterion requiring two consecutive and rising AdV viremia results exceeding 1,000 copies/mL, the two consecutive viremia results used to determine eligibility must have been assayed at the same laboratory, preferably the central laboratory however, local lab results are also acceptable (with Medical Monitor approval). This process is expected to expedite the randomization and dosing of participants whose clinical status may rapidly deteriorate. A central laboratory blood sample must be collected prior to dosing on Day 1. All study analyses will continue to be performed using viral load data from the central laboratory.

Participants will be followed weekly for viremia and viral load in the stool while symptomatic. For participants who require intubation and/or undergo bronchoscopy with bronchoalveolar lavage (BAL), a sample of BAL fluid should, when possible, be obtained for AdV viral load determination at the central laboratory. For participants who develop symptoms and/or signs of possible AdV-associated neurological disease, and whose treating physician determines that laboratory evaluation of cerebrospinal fluid (CSF) for diagnostic and/or monitoring reasons is clinically indicated, CSF samples for AdV viral load determination should, when possible, be sent to the central laboratory. In all cases, BAL and CSF samples required for routine clinical care of the patient take precedence over these study-related evaluations.

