The body of published data supports the concept that virological suppression translates into clinical benefit. This view is also robustly expressed in AdV consensus treatment guidelines such as those of ECIL-4 ([Matthes-Martin 2012](#)) and EBMT ([Hiwarkar 2018](#)), recommending pre-emptive therapy, which is based on a recognition of the surrogacy of viremia.

Since there are no approved antiviral therapies for the treatment of AdV, the kinetics of therapeutic viremia resolution are not established. Data from the CHARMS study, in which patients with persistent and/or recurrent viral infections were treated with posoleucel provide an indication of viral load kinetics that have informed the selection of the Day 29 post-treatment

timepoint for the evaluation of the primary efficacy outcome in the current study. In the CHARMS study, there were 13 participants with informative AdV viremia data; 9 of these participants demonstrated declines in viremia after administration of posoleucel. In all cases, these viremia responses were apparent by 4 weeks (ie, 28 days) of treatment with posoleucel. Accordingly, the evaluation at Day 29 (ie, 28 days after the initial infusion of posoleucel/placebo) has been selected for the primary efficacy outcome in the current study.

It is generally accepted that the magnitude and duration of AdV viremia contribute to the development of clinically relevant infections ([Sedlacek 2019](#)), and that the overall AdV viral burden (extent of viremia over time) is predictive of all-cause mortality in pediatric HCT recipients with AdV viremia ([Zecca 2019](#)). The levels of AdV viremia required for inclusion in this study have been selected because these are thresholds that place patients at risk for development of disseminated AdV disease and increased mortality ([Hiwarkar 2018](#), [Mynarek 2014](#)) and are less likely to be associated with spontaneous resolution. Importantly, AdV unlike CMV or EBV, is a lytic virus so risk of recurrent infections once the virus has cleared is considered to be low. Nonetheless, to assess durability of response longer term data on viremia as well as signs and symptoms will be captured.

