### 6.1 Inclusion Criteria

Patients must meet all of the following criteria in order to be eligible for enrollment into the study. Screening laboratory criteria can be confirmed using local or central laboratories.

1. Male or female of any age.
2. Has undergone allogeneic (including umbilical cord) cell transplantation  $\geq 21$  days prior to dosing and has demonstrated engraftment with an absolute neutrophil count  $>500/\text{mm}^3$ , AND has one of the following:
  - a. AdV viremia DNA  $\geq 10,000$  copies/mL at screening, OR
  - b. Two consecutive and rising AdV viremia DNA results of  $\geq 1,000$  copies/mL at screening, AND
    - i. has absolute lymphocyte count  $<180/\text{mm}^3$ , OR
    - ii. has received T cell depletion, OR
    - iii. had a cord blood transplant.
3. Males and females of childbearing potential who engage in heterosexual intercourse must agree to use contraception as detailed in [Appendix 5](#) of this protocol and refrain from donating sperm or eggs for at least 90 days after treatment completion.
4. Willing and able to provide signed informed consent.
5. Has an HLA type matching with at least 1 suitably matched and available posoleucel VST line for infusion.

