### **Added analysis window for primary and secondary AdV viral load endpoints**

**Rationale:** The rationale for selection of Day 29 for the primary and secondary AdV viral load endpoints were based on the results from the Phase 2 CHARMS study, reference Section 5.4 above. The two AdV assays used in CHARMS had a higher lower limit of quantitation (LLOQ) of 172 and 190 copies/mL as compared to the assay used in this Phase 3 study with an LLOQ of 32 copies/mL. Review of blinded data in patients with declining AdV viremia showed a delay in reaching <LLOQ beyond Day 29 in some patients. This window would allow the last observed result to be used for primary endpoint analysis when applying this more sensitive assay.

- **Other changes:**

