3.1.3 Definition of Baseline

Baseline is defined as the last non-missing measurement prior to the first dose of study treatment. This can be on Day 1 as long as the measurement is taken prior to the first dose.

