3.4.1 Primary Efficacy Endpoint Analysis

3.4.2 Primary Analysis of Primary Efficacy Endpoint

The primary efficacy endpoint, undetectable viremia (less than LLOQ) at Day 29 of the Primary Study Period, will be summarized by treatment group using the count and percentage, together with an exact (Clopper-Pearson) 95% confidence interval for the true percentage. The difference in percentages between the two treatments (posoleucel – placebo), together with a 95% exact confidence interval for the true difference, will be presented.

This endpoint will be analyzed using logistic regression. The model will include a term for treatment and the following covariates: level of viremia at Baseline ($\geq 10,000$ copies/mL or $< 10,000$ copies/mL AdV DNA), age (≥ 12 years or < 12 years) and absolute lymphocyte count at Baseline. For participants who discontinued treatment but remain on the study, data collected after treatment discontinuation will be included in the analysis. If a participant doesn't have plasma AdV DNA result in the Day 29 through Day 43 window but has undetectable viremia before Day 29 and after Day 43, it will be imputed as success for the primary endpoint. The deaths related to adenovirus infection on or before Day 29 will be imputed as failure.

Subgroup analyses of the primary endpoint will be performed for both of the randomization stratification variables: (1) level of viremia: $\geq 10,000$ copies/mL and $< 10,000$ copies/mL AdV DNA and (2) age: ≥ 12 years or < 12 years.

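### The primary logistic model uses baseline viral load only as above or below 10,000 copies/mL, a modest loss of efficiency that one added continuous term would reduce

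*SAP*

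**What the plan says.** SAP 3.4.2 and protocol 10.3.1.1 give the same primary model, a logistic regression: "The model will include a term for treatment and the following covariates: level of viremia at Baseline", entered as two categories cut at 10,000 copies/mL, together with age in two categories, "and absolute lymphocyte count at Baseline". Lymphocyte count has no cut-point and so reads as continuous. The SAP plans subgroup analyses for "both of the randomization stratification variables: (1) level of viremia" and age, which explains why the binary viremia term is in the model.

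The quantitative value exists. The protocol synopsis (Assessment Overview) says "A central laboratory blood sample must be collected prior to dosing on Day 1", and SAP 3.1.3 says "Baseline is defined as the last non-missing measurement prior to the first dose of study treatment". Protocol 10.3.1.3 already uses load on the log10 scale for the time-averaged area endpoint. No model with continuous baseline load is described, either as primary or as a sensitivity analysis.

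Protocol 6.1 gives two virologic routes into the trial. One is a load of at least 10,000 copies/mL, with no upper limit. The other, for participants with an added risk factor, is "Two consecutive and rising AdV viremia DNA results of" at least 1,000 copies/mL. The Amendment 3 rationale in protocol Appendix 10 describes "the assay used in this Phase 3 study with an LLOQ of 32 copies/mL", and that limit defines clearance.

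**The concern.** The endpoint asks everyone to reach the same absolute level, wherever they started. A participant entering at 10^6 copies/mL has two log10 further to fall than one entering at 10^4, yet the model treats them as the same. If starting load predicts Day 29 clearance, the binary term removes only part of the variation that the measured value could explain. It also leaves the adjusted comparison open to chance imbalance in load within the upper category.

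The documents give some reason to expect a link. Protocol 5.4 says that "the magnitude and duration of AdV viremia contribute to the development of clinically relevant infections" and ties overall viral burden to mortality. Amendment 4 added lymphocyte count because it was believed to be a strong predictor, so the sponsor has already accepted a prognostic covariate beyond the stratification factors. At stake is some power for the protocol's planned test and some precision on the risk-difference scale.

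**Working it through.** **The plan's own figure.** Protocol 10.1 uses rates of 0.55 and 0.25, two-sided alpha 0.05, 80% power and a chi-square test; the synopsis gives 1:1 allocation. With mean rate 0.40, n per arm = [1.960 × √(2 × 0.40 × 0.60) + 0.842 × √(0.55 × 0.45 + 0.25 × 0.75)]² / 0.30² = (1.358 + 0.555)² / 0.09 ≈ 40.7, so 41 per arm and 82 in total. This matches the protocol; power at 41 per arm is 80.3%. The calculation assumes no covariate adjustment. SAP 2.2.4 prints 0.50 for posoleucel with the same 82, a separate discrepancy; the protocol's 0.55 is used here.

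**Fall needed to reach the threshold.** log10(32) ≈ 1.5. The required falls are:
- from 10^3: 3 − 1.5 = 1.5 log10
- from 10^4: 4 − 1.5 = 2.5 log10
- from 10^6: 6 − 1.5 = 4.5 log10
- from 10^7: 7 − 1.5 = 5.5 log10

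The upper category therefore pools falls that can differ by 2 to 3 log10.

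**Effect of adding the continuous term.** The documents give neither the distribution of baseline load nor its association with clearance, so both are assumed: log10 load normal with mean 4.5 and SD 1, truncated at 3. This puts 74% of participants at or above 10,000, and the binary term then keeps about 51% of the variance in log10 load. The simulation used N = 82, 55% vs 25% clearance, one-sided 0.025, and age and lymphocyte terms in the model with no effect. The power columns use 2,000 trials per row. The standard errors come from a separate 2,500 trials per row with the same set-up.

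| Odds ratio of clearance per log10 higher load | Power, binary term | Power, continuous term added | Change (points) | Median SE of log odds ratio, binary → added |
|---|---|---|---|---|
| 0.61 | 81.4% | 81.2% | −0.2 | 0.513 → 0.527 |
| 0.37 | 81.6% | 83.2% | +1.6 | 0.535 → 0.567 |
| 0.22 | 85.6% | 88.4% | +2.8 | 0.571 → 0.629 |
| 0.14 | 87.0% | 90.7% | +3.7 | 0.606 → 0.698 |

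The Monte Carlo error of one power figure is about √(0.82 × 0.18 / 2,000) ≈ 0.9 point. Across these rows the variance of a standardised (g-computed) risk difference is 1 to 11% lower with the continuous term. A run without the age and lymphocyte terms gave 14% lower at the strongest association. With no association (odds ratio 1) it gave 1% higher variance and power of 82.5% vs 81.7%.

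**Sensitivity to the share above the cut.** Here log10 load replaced the binary term instead of being added to it. With 60%, 75% or 90% of participants above the cut, the binary term keeps about 60%, 50% or 32% of the variance in log10 load. At an odds ratio of 0.25 per log10 (4 in the other direction), power goes from 85.2 to 86.6%, 84.4 to 88.5% and 83.5 to 90.3%, gains of 1.4, 4.1 and 6.8 points. At 0.67 per log10 the gain is at most 0.5 point.

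**Chance imbalance.** Under the main assumptions, the between-arm difference in mean log10 load within the upper category has SD 0.18, so differences up to about 1.96 × 0.18 ≈ 0.35 log10 are ordinary.

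**The case against.** The binary term is a stratification factor, and adjusting for it is standard and valid. A statistician could reasonably leave the model as it is. A reader might infer from the concern that the planned analysis is biased or its test invalid; nothing in the documents supports that.

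A reader might also infer that the continuous term tightens the reported treatment estimate at no cost. It does not tighten the estimate that the model produces. The treatment coefficient is a conditional log odds ratio, and its standard error rises. At an odds ratio of 0.22 per log10, the ratio of upper to lower 95% limits, exp(2 × 1.96 × SE), widens from 9.4 to 11.8. Power rises because the conditional effect moves further from zero (non-collapsibility). The precision gain belongs to a standardised risk difference, which neither document plans.

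Nor is the term free. The interim was planned at about 40 participants and the SAP says the study was terminated for futility; the final number is not given. If it were 42, there would be about 42 × 0.40 ≈ 17 clearances for a model that already has four terms. In that setting, at an odds ratio of 0.61, power is about 51% with either model. The median log odds ratio is 1.60 with the added term and 1.51 without it, against a true 1.35. At 0.14, about 12 to 14% of fits fail to converge with either model.

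A third tempting inference is that the cut at 10,000 barely separates participants. The documents do not give the share above it, and under the main assumptions the binary term keeps about half the variance. Protocol 5.4 links viremia to clinical infection and mortality, not to Day 29 clearance, so the strength of that link is assumed.

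Finally, the SAP states that no hypothesis tests will be performed, and its percentages, exact intervals and interval for the difference do not use the covariate.

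All of this stands. It limits the size and reach of the point, but a collected quantitative value is still used only in two categories.

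**Conclusion.** The point holds as a modest loss of efficiency. Under the main assumed load distribution with 82 participants, power for the protocol's test changes by about 0 points if load is weakly prognostic and rises by about 2 to 4 points if the association is moderate to strong. The variance of a standardised risk difference falls by about 0 to 11%. The range includes no gain, and it depends on an assumed load distribution and an association that the documents do not quantify. In the SAP as written, what remains is the adjusted estimate and its protection against chance imbalance in load. The power figures bear on the protocol's test, or on a later trial that reuses this model.

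**What to change.** Keep the 10,000 copies/mL stratification term and the subgroup display, and add continuous baseline log10 AdV DNA from the central laboratory to the logistic model. If treatment codes are already known, leave the primary model unchanged and report the extended one as a labelled sensitivity analysis. State whether the reported effect is a conditional odds ratio or a standardised risk difference, since the added term changes the first and can sharpen the second. Summarise log10 baseline load by arm as well: SAP 3.3.2 lists baseline viremia only as counts and percentages, which may not show imbalance within the upper category.

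The cost is one degree of freedom and a few lines of SAP text, with no new data. If the final sample is near 40, that degree of freedom weighs more, and the sensitivity-model route is the safer one.

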3.5 Safety Analyses

Safety will be analyzed and compared between treatments received based on data from the Primary Study Period. No formal comparisons will be made between these groups.

All safety analyses will be based on the Safety Population.

Categorical endpoints will be summarized using the number and percentage of participants within each category. Continuous endpoints will be summarized descriptively with summary statistics (number of non-missing observations, arithmetic mean, standard deviation, median, minimum, and maximum).

3.5.1 Adverse Events (AEs)

All AEs will be coded to system organ class and preferred term using MedDRA. A treatment-emergent adverse event (TEAE) is defined as an adverse event with a start date and time on or after the administration of investigational product or placebo or that worsened in severity after administration of investigational product or placebo through the end of the study.

An overall summary of AEs will be provided with the number and percentage of participants who experienced at least one (1) AE or TEAE in the following categories:

- Any TEAEs
- Any TEAEs by severity
- Any treatment-related TEAEs
- Any treatment-related TEAEs by severity
- Any treatment-emergent AESI (TEAESIs)
- Any treatment-emergent serious AEs (TESAEs)
- Any treatment-related TESAEs
- Any TEAEs leading to discontinuation of study treatment
- Any TEAEs leading to discontinuation of study, and
- Any AEs leading to death

The numbers and percentages of participants will also be presented by system organ class (SOC) and preferred term (PT) for each of the TEAE categories in the summary. Participants with multiple AEs will be counted only once per SOC and PT.

Listings will be presented specifically for any AEs, SAEs, AESIs, and AEs leading to discontinuation of study treatment and study.

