
 
To assess length of hospital stay, days spent in the intensive care unit (ICU), hospital readmission, the need for mechanical ventilation, and the need for supplemental oxygen.
 
	
 
Number of days in the hospital (for any reason including, but not limited to, AdV) during the study.
 
Number of days in the hospital due to AdV-related infection.
 
Number of hospitalizations/re-hospitalizations for any reason during the study.
 
Number of days spent in the ICU during the study.
 
Proportion of participants who need mechanical ventilator support, and number of days ventilator support is required during the study.
 
Proportion of participants who require supplemental oxygen to maintain SpO2 >90%, and number of days supplemental oxygen is required during the study.
 

 
To evaluate the persistence of posoleucel cells.
 
	
 
Persistence of posoleucel cells.
 

 
To determine the viral re-activation and disease occurrence due to BK virus (BKV), cytomegalovirus (CMV), human herpesvirus 6 (HHV-6), Epstein-Barr virus (EBV), or John Cunningham virus (JCV).
 
	
 
Proportion of participants who develop viremia and/or clinical disease (per Investigator assessment) by Day 29 (due to BKV, CMV, HHV-6, EBV, and/or JCV) for those participants without viremia at randomization.
 
Proportion of participants with resolution of viremia by Day 29 (due to BKV, CMV, HHV-6, EBV, and/or JCV) for those participants with viremia at randomization.
 

 
To evaluate non-relapse and all-cause mortality.
 
	
 
Non-relapse mortality at Week 24.
 
All-cause mortality at Week 24.
 
Death due to AdV disease.
 

 
To determine the percent of participants who have clearance of AdV in a) stool, and b) nasopharyngeal swab at Day 29.
 
	
 
Proportion of participants with undetectable AdV viral load (less than LLOQ) in a) stool, and b) nasopharyngeal swab at Day 29.
 

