#### 10.3.2 Analysis of Safety

Safety will be analyzed and compared between treatment received based on data from the Primary Study Period. In addition, for purposes of complete reporting, safety will be reported for data from the Cross-Over Period by treatment received in the Cross-Over Period, but no comparisons will be made between the two treatments.

The primary safety endpoint is the incidence and severity of TEAEs, including individual AESIs, during the study. The safety profile will be further assessed based on changes in clinical laboratory assessments, vital signs, ECGs, and physical examinations. All safety analyses will be based on the Safety Population.

Safety analyses in general will be descriptive and will be presented by study period (Primary Study Period or Cross-Over Period) and treatment group or cross-over group in a tabular format. Categorical endpoints will be summarized using number and percentage of participants within each category. Continuous endpoints will be summarized descriptively with summary statistics (number of non-missing observations, mean, standard deviation, median, minimum, and maximum).

A TEAE is defined as an adverse event with a start date and time on or after the administration of investigational product or placebo or that worsened in severity after administration of investigational product or placebo through the end of the study. For AEs with a missing start date, the AE will be considered treatment-emergent unless there is additional information indicating that the AE started prior to study treatment. The number and percentage of participants with TEAEs will be tabulated by Medical Dictionary for Regulatory Activities (MedDRA) System Organ Class and Preferred Term for each treatment group/cross-over group. This will be done overall, by severity, and by relationship to treatment. Adverse events leading to discontinuation of the study, SAEs, and AESIs will be summarized by treatment group. By-participant listings will also be provided for any deaths, SAEs, AESIs, and adverse events leading to discontinuation of study drug.

The incidence and severity of acute GVHD during the study, the incidence and severity of chronic GVHD during the study, the incidence and severity of CRS during the study, and the incidence and severity of any treatment-emergent AESIs during the study will each be

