### **Events NOT Meeting the AE Definition**

- Any clinically significant abnormal laboratory findings or other abnormal safety assessments which are associated with the underlying disease, unless judged by the Investigator to be more severe than expected for the participant's condition.
- The disease/disorder being studied or expected progression, signs, or symptoms of the disease/disorder being studied, unless more severe than expected for the participant's condition.
- Medical or surgical procedure (eg, endoscopy, appendectomy): the condition that leads to the procedure is the AE.
- Situations in which an untoward medical occurrence did not occur (social and/or convenience admission to a hospital).
- Anticipated day-to-day fluctuations of pre-existing disease(s) or condition(s) present or detected at the start of the study that do not worsen.

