1 INTRODUCTION

This document details the analysis plan for the study entitled “Phase 3, Randomized, Double-Blind, Placebo-Controlled Trial, with Cross-Over, of Posoleucel (ALVR105) for the Treatment of Adenovirus Infection in Pediatric and Adult Participants Receiving Standard of Care Following Allogeneic Hematopoietic Cell Transplantation”. It is based on Protocol P-105-303 Amendment 4 dated 30 November 2023 and describes the proposed efficacy and safety analyses. Since the study is terminated due to futility, only the primary efficacy endpoint and selected safety endpoints will be analyzed.

The Statistical Analysis Plan (SAP) will be finalized prior to interim database lock. After the database lock, any deviation from the SAP will be documented in the final Clinical Study Report (CSR).

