2.3.2 Safety Endpoints

The safety endpoint is the incidence and severity of TEAEs, including adverse events of special interest (AESIs), during the study.

The clinical laboratory evaluations (hematology, chemistry, and urinalysis) will also be summarized.

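### SAP 3.5.1 leaves out the deaths listing that the protocol promises and shows fatal outcomes only through AE records, so some adenovirus deaths may be absent from the by-arm safety summaries

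*SAP*

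**What the plan says.** The protocol plans to report deaths in two ways. Section 4 lists mortality among the exploratory endpoints, including "All-cause mortality at Week 24", non-relapse mortality at Week 24 and death due to adenovirus disease. Section 10.3.2, on safety, adds: "By-participant listings will also be provided for any deaths, SAEs, AESIs, and adverse events leading to discontinuation of study drug".

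The final SAP was written after the trial stopped for futility. It narrows the scope in its Section 1: "only the primary efficacy endpoint and selected safety endpoints will be analyzed". Section 2.3.2 then defines what is left on the safety side: "The safety endpoint is the incidence and severity of TEAEs, including adverse events of special interest (AESIs), during the study", with clinical laboratory evaluations added. Section 3.5.1 contains one category named for a fatal outcome, "Any AEs leading to death". Its listings sentence reads: "Listings will be presented specifically for any AEs, SAEs, AESIs, and AEs leading to discontinuation of study treatment and study". Deaths, which the protocol's corresponding sentence includes, are not there.

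Protocol Appendix 4 sets what counts as an AE. Among the events that do not count is: "The disease/disorder being studied or expected progression, signs, or symptoms of the disease/disorder being studied, unless more severe than expected for the participant's condition".

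**The concern.** Death from any cause is the safety outcome that depends least on judgment, and the population is severely ill. If the only route into the safety tables is an AE record, the number of deaths shown per arm depends on whether each site regarded a fatal adenovirus course as expected progression or as something worse. In arms this small, one or two deaths that never reached the AE record could change how the safety comparison reads, in either direction.

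Cross-over adds to this. A participant may cross over only after developing target organ disease or after existing disease has progressed, so those who do are a high-risk group. Deaths in that group fall outside the period that the AE summaries cover.

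**Working it through.** No arithmetic applies. The check is whether any planned output shows every death by arm.

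**Step 1. What each SAP output can show**

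| Output | Section | Requires an AE record? | Limits |
|---|---|---|---|
| AEs leading to death | SAP 3.5.1 | Yes | Primary Study Period data |
| TEAEs by severity (Grade 5) | SAP 3.5.1; grading in protocol Appendix 4 | Yes | Primary Study Period data |
| Treatment-emergent serious AEs | SAP 3.5.1 | Yes | Primary Study Period data; deaths not separated from other serious events |
| AE and SAE listings | SAP 3.5.1 | Yes | No by-arm count; deaths not listed as such |
| AESI summaries | SAP 3.5.2 | Yes | Both periods, but only GVHD, CRS, infusion-related events, and graft failure or rejection |
| Disposition table and listing | SAP 3.3.1 | No | Death not named as a reason; no cause; not a safety output |
| Primary endpoint | SAP 3.4.2 | Not stated | Adenovirus-related deaths to Day 29 become failures; no death count shown |

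Every safety output depends on an AE record. The two outputs that may not do so are not safety outputs, and neither is specified to show a count of deaths.

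**Step 2. Can a death fall outside the AE record?** Appendix 4 takes the disease under study and its expected progression out of AEs, with an exception for a course more severe than expected. It defines an SAE as a serious AE. The criterion of resulting in death therefore applies only to something that is already an AE, and cannot bring an excluded event back in. The protocol's own background (Section 3.2) cites mortality of up to 50% once adenovirus disease develops, so a site could reasonably regard a fatal course as within expectation.

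**Step 3. Is there a rule that catches all deaths?** Three places come close.
- Protocol 9.2.1 mentions death when discussing SAEs, but only for participants who have left the study and only for events judged reasonably related.
- Appendix 4 asks for post-mortem findings when a participant dies. That is a follow-up duty, and it does not classify the death as an SAE.
- Protocol 8.2 gives reasons for withdrawal from the study, and death is not among them.

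None says that every death is recorded as an SAE.

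**Step 4. Period covered.** SAP 3.1 and 3.5 base the safety summaries on the Primary Study Period. Only the AESIs in 3.5.2 are also summarized by cross-over group. A death after cross-over, even one recorded as an AE, has no death summary. It could appear in the AE and SAE listings, or within the AESI severity counts if the fatal event was itself an AESI.

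**Step 5. Is there material for a fuller report?** At least in part. Protocol 9.1.2 puts death due to adenovirus disease before the Adjudication Committee, Appendix 8 defines it as proven or probable, and SAP 3.4.2 already needs adenovirus attribution and timing to Day 29. This does not show that later deaths or other causes are held in analyzable form.

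**The case against.** There is a fair case that little is lost.

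- **Appendix 4 may capture most of these deaths.** It has the exception for a course worse than expected. It also counts as AEs new conditions diagnosed after treatment and exacerbations of pre-existing chronic or intermittent ones. A participant with viremia who then develops fatal pneumonia or hepatitis plausibly qualifies. Death is the first seriousness criterion, and the request for post-mortem findings suggests that deaths were meant to enter SAE reporting. This stands as a reason why omission is possible rather than certain. The CRF and its completion instructions are not available to settle it.
- **Disposition outputs may show deaths.** SAP 3.3.1 covers reasons for leaving the study in both periods and adds by-participant listings. That stands too, but only if the CRF offers death as a reason, and it would not give cause.
- **The narrower scope is deliberate and disclosed.** Dropping exploratory mortality endpoints after a futility stop is not in itself an error. That reasoning does not extend to the deaths listing, which the protocol placed under safety.

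A reader might go further and infer that adenovirus deaths will be missing, or put a number on them by applying the 50% mortality figure to the planned 41 per arm. The documents support neither. Whether a death is omitted depends on site judgment. The 50% is a rate after progression to adenovirus disease, not a rate for everyone randomized. The trial stopped for futility, and its final enrollment is not stated. The share of deaths due to adenovirus is not given either.

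A reader might also want Appendix 4 rewritten. In a terminated trial that would not change how past deaths were recorded.

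**Conclusion.** The point holds in a limited form. The SAP omits a safety listing that the protocol promises, and no planned safety output counts deaths independently of the AE record. Some adenovirus deaths may therefore be absent from the by-arm safety summaries. Deaths after cross-over have no planned death summary, whether or not they were recorded as AEs.

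No size can be attached. The conclusion rests on the text of SAP 3.3.1, 3.5, 3.5.1 and 3.5.2 and protocol 10.3.2 and Appendix 4, and on the assumption that no unseen CRF instruction required every death to be entered as an SAE. If such an instruction exists, the gap before cross-over reduces to the missing listing, and the gap after cross-over remains. The primary efficacy definition is not affected. This should be corrected in the safety reporting.

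**What to change.** In SAP 3.5:

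1. Restore the by-participant listing of all deaths from protocol 10.3.2, whether or not the death was recorded as an AE.
2. Add one table of all deaths regardless of AE status, by treatment arm and study period (before and after cross-over), with cause where recorded: adenovirus-attributable by the Appendix 8 definition, relapse, other, or not recorded.

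If the database is already locked, SAP Section 1 provides the route: record the addition as a deviation from the SAP in the CSR.

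No change to Appendix 4 is needed, because the table does not depend on AE classification. The cost is one extra table, one extra listing and some reconciliation of death records with the AE data. Where cause was not collected, the table should say so rather than assign one.
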